## 8.5 Off study criteria

A patient will be considered off study under the following circumstances:

1. The patient is withdrawn from the study prior to administration of transduced CD34+ cells
2. The patients/parent/guardian withdraws consent for study procedures and data collection
3. The patient is lost to follow-up

#### **8.6 Follow-up of withdrawn subjects**

Patients withdrawn from the study prior to administration of transduced CD34+ cells and patients for whom consent has been withdrawn for the study, will resume normal clinical care. Efficacy and safety assessments will not be carried out from the point of withdrawal and data will not be recorded in the Case Report Forms (CRFs).

#### **8.7 Definition of end of trial**

- The sponsor will notify GTAC and the MHRA of the end of the study within a period of 90 days.
- The end of the study is defined as the last patient's last scheduled visit according to the protocol, which will be the 3-year follow-up visit of the last patient entered into the trial.
- In case the study is ended prematurely, the sponsor will notify GTAC and the MHRA within 15 days, including the reasons for the premature termination.
- Within one year after the end of the study, the investigator/sponsor will submit a final study report with the results of the study, including any publications/abstracts of the study, to GTAC and the MHRA.

#### **8.8 Trial stopping criteria**

The trial will be stopped prematurely under the following circumstances:

1. Evidence of oncogenesis in any trial patient. The trial will only be re-started following agreement from both the MHRA and GTAC.

The events below will result in halting of the trial and will require a formal evaluation of the reasons for non-efficacy. The trial will only be re-started after discussion with and approval from the MHRA and GTAC:

1. Unsuccessful transduction of 3 consecutive patient CD34+ cells to specified criteria
2. No evidence of vector integration in 3 consecutive patients at 6 months post-treatment
3. 3 consecutive patients needing to re-start enzyme replacement therapy prior to 1 year post-gene therapy

*(From our experience of these studies, 3 consecutive patients would be seen as a number whereby this could not have happened by chance and is most likely related to processes or procedures)*

4. Emergence of new therapies for ADA-SCID, believed by the CI to be of greater benefit to this population of trial patients. The CI is in regular contact with other experts in the field of ADA-deficiency therefore is aware of new developments in the field. Regular reviews of the currently available treatment options for the subject population will be conducted by the PI throughout the trial.

Complete cessation of the trial would be made in consultation with the MHRA and GTAC.

## 8.9 Statistical analysis

### Timing of analyses

One interim analysis, one primary analysis, one longer term follow-up and one end-of-study analysis are planned for this study.

An interim look will be done when all on-study patients (not including CUP) have reached at least 6 months' follow-up.

The primary analysis for the study will be done when all on-study patients have reached at least 12 months' follow-up. This interim analysis will be including CUP and HSCT groups.

The third analysis will be done when all IMP on-study patients have reached at least 24 months' follow-up. This interim analysis will be including CUP and HSCT groups.

The final analysis will be done at the end of the study. i.e. after on study patients, have completed the planned follow up of 3 years. This analysis will also include HSCT group.

#### 8.9.1 Analysis populations

There will be 3 populations analysed in this study: The on-study patients treated with IMP (gene therapy), patients who were treated under compassionate use (CUP patients) and the historical comparator group of patients who received HSCT.

The safety analysis population will include all patients who received the IMP infusion, including both on-study patients and patients who were treated on a compassionate use basis. In addition, all the allogeneic HSCT controls patients (with any type of donor) will be included.

Further efficacy populations will be detailed in the statistical analysis plan (SAP).

### **8.9.2 Data analysis/description**

Descriptive statistics will be employed for the socio-demographic characteristics of the study population.

The primary efficacy endpoints, overall survival (OS) and event-free survival (EFS) will be compared descriptively to a group of ADA-SCID patients treated by allogeneic HSCT (historical control group). The main secondary endpoint, will be summarised descriptively.

Data will be summarized in tables displaying the mean, standard deviation, median, minimum, maximum and number of subjects per group for continuous data (e.g. age, weight) or in tables displaying count and percentage for categorical data (e.g. gender, previous treatment). Data will be presented by visit, if applicable. Data listing by subject will be provided as appropriate.

All statistical analyses will be performed and data appendices will be created using SAS® version 9.4 or higher

#### **Safety**

Safety will be analysed descriptively by arm and study phase using the safety analysis population. Coding will be done using MedDRA version 18.1 or higher. The safety of treatment will be summarised using AEs, laboratory assessments and clinical examination assessments. These will be analysed continuously from pre-gene therapy to study completion, depending on the data available. Further details are given in the SAP.

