## Trial design and methods: Summary flowchart of the patients treated with gene therapy

**Recruitment period:** 5 years

**Trial duration per participant:** From consent until 3 years post-infusion of transduced CD34+ cells

**Estimated total trial duration:** 8 years

**Planned trial sites:** Great Ormond Street Hospital for Children NHS Foundation Trust (single-site trial)

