#### **4.2.2 Secondary objectives**

The secondary objectives are to:

- Compare survival and event free survival at 2 and 3 years between patients treated with IMP and patients treated with allogeneic HSCT
- Determine the percentage of IMP treated patients requiring immunoglobulin replacement therapy at all evaluation points from 18 months onwards
- Compare frequency of infections, and growth of pathogenic microorganisms over 3 years
- Evaluate the longitudinal clinical effect in terms of improved immunity
- Evaluate tolerability of conditioning regimen. These data will be reviewed and interpreted by the PI and the study team
- Evaluate feasibility of the transduction procedure. These data will be reviewed and interpreted by the PI and the study team

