## **10.8 Name of each NIMP**

- Cotrimoxazole
- Itraconazole
- Penicillin
- Aciclovir
- Immunoglobulin
- Calcium Folinate
- Busulfan

NIMP suspected Adverse Drug Reactions (ADR) or side effects will be reported through the yellow card system.

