#### ***Blood and the lymphatic system disorders:***

Myelo-suppression and immuno-suppression were the desired therapeutic effects of the conditioning regimen. Therefore all patients experienced profound cytopenia: leukopenia 96%, thrombocytopenia 94% and anemia 88%. The median time to neutropenia was 4 days for both autologous and allogeneic patients. The median duration of neutropenia was 6 days and 9 days for autologous and allogeneic patients.

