#### 8.4.1.1 Definition of Treatment-emergent Adverse Events

Adverse events (AEs) will be summarised on the basis of treatment emergence. An adverse event is considered to be treatment emergent if it occurred on or after the date and time of the start of the IMP infusion. If the start time of the event is not present, any event starting on the same day as the infusion will be considered to be treatment emergent. If the start date of the adverse event is partial or missing, it will be considered to be treatment emergent if:

- the day is missing, the month and year are present and are the same as or after the month and year of the infusion and the end date is missing or is not before the date of infusion,
- the day and month are missing, the year is present and is the same as or after the year of the infusion and the end date is missing or is not before the date of infusion,
- the entire date is missing and the end date is missing or is not before the date of infusion.

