#### 8.4.1.2 Adverse Events

Treatment emergent adverse events will be summarised for each of the IMP treated groups in an overall summary presenting the number (%) of subjects with:

- any AE,
- moderate or severe AE,
- severe AE,
- treatment related AE (possibly/probably/definitely/not assessable/missing),
- AE leading to study withdrawal,
- any serious adverse event (SAE),
- treatment related SAE,
- SAE leading to death.

Incidence and frequency of treatment emergent AEs will be summarised for each of the IMP treated groups by system organ class (SOC) and preferred term (PT):

- overall,
- by maximum severity,
- by maximum relationship to treatment,
- treatment related AEs,
- AEs leading to study withdrawal (if sufficient events).

In addition, a summary table for the most frequently reported treatment emergent adverse events (those reported in 2 or more subjects) will be presented by PT in descending order of incidence and frequency.

In each table, if the same SOC or PT is reported on multiple occasions for a single subject, it will only be included once in the summary. In the table by maximum severity, only the most severe occurrence for each SOC and PT for each subject will be included in the summary. In the table by maximum relationship, only the most related occurrence for each SOC and PT for each subject will be included in the summary.

Any adverse events that are not treatment emergent (occurred prior to the infusion) will be listed.

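### Protocol 8.9.2 promises safety by study phase, but the SAP's AE and SAE tables use one undivided post-infusion window and count each term once per child, so a later repeat of an early term usually leaves them unchanged

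*Protocol*

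**What the plan says.** The Safety paragraph of Protocol 8.9.2 commits to a split: "Safety will be analysed descriptively by arm and study phase using the safety analysis population". It leaves the detail to the SAP.

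SAP 8.4.1.1 calls an event "treatment emergent if it occurred on or after the date and time of the start of the IMP infusion". It gives no closing date and no sub-periods. Participation runs "From consent until 3 years post-infusion of transduced CD34+ cells" (Protocol, Summary), so the window is in effect months 0 to 36. Events that start before infusion are listed, not tabulated.

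SAP 8.4.1.2 opens its tables with: "Incidence and frequency of treatment emergent AEs will be summarised for each of the IMP treated groups by system organ class" and PT. The counting rule follows: "if the same SOC or PT is reported on multiple occasions for a single subject, it will only be included once in the summary". The maximum-severity and maximum-relationship tables keep only the worst or most related occurrence per child. SAP 8.4.1.3 repeats these rules for SAEs. The change history in SAP section 10 records no decision to drop a phase split.

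A secondary objective in Protocol 4.2.2 is: "Evaluate tolerability of conditioning regimen". SAP 4.2 leaves those data to the investigator and study team, and SAP 8.2.13 summarises conditioning exposure, not toxicity.

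**The concern.** Busulfan is given before the cells, with a wash-out of at least 24 hours (Protocol 7.5.6). Appendix 6 reports a median of 4 days to neutropenia, without stating the reference day. Conditioning effects that appear after infusion therefore share one window with everything that happens over the next three years.

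The two ends of that window answer different questions. The first weeks bear on tolerability of conditioning. Later follow-up bears on the safety of an integrating vector. Under the once-per-child rule, a term recorded in the first weeks has used up that child's place in its row. A second episode of cytopenia, fever or infection in year 2 under the same PT adds nothing to the incidence table. A new PT within an SOC already counted leaves the SOC row unchanged. No planned AE or SAE table separates the early post-conditioning period from later follow-up, which is what the phrase in Protocol 8.9.2 leads a reader to expect.

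**Working it through.** The documents give no safety-precision figure to reproduce. Two Appendix 6 fractions were checked and agree with the text: 49/55 = 89.1% and 40/103 = 38.8%.

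**Inputs**
- n = 10 on-study children (SAP 7.1).
- e, the proportion of children with a given term early after infusion. Appendix 6 gives adult cytopenias ("leukopenia 96%, thrombocytopenia 94% and anemia 88" per cent), paediatric infection including febrile neutropenia 89%, paediatric mild or moderate fever 76%, and adult infection 39%. These are label data used as a range, not rates from this trial.
- l, the proportion with the same term later. The documents do not give it. 20% is assumed for illustration, independent of the early event.

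**Without any assumption on rates.** If 9 of 10 children have the term early and 3 of 10 have it late, the pooled row shows at least max(9, 3) = 9 and at most min(10, 9 + 3) = 10. The 3 late cases move the row by 0 or 1.

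**Under independence**
- Pooled row shows 1 − (1 − e)(1 − l).
- Late cases that add to the row: n(1 − e)l.
- Late cases hidden: n·e·l.
- Share of late cases hidden: n·e·l / (n·l) = e, whatever l is.

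With n = 10 and l = 20%, a by-phase table would show 2 late cases on average:

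| e | Pooled row shows | Late cases added | Late cases hidden | Share hidden |
|---|---|---|---|---|
| 39% | 51.2% | 1.22 | 0.78 | 39% |
| 76% | 80.8% | 0.48 | 1.52 | 76% |
| 89% | 91.2% | 0.22 | 1.78 | 89% |
| 96% | 96.8% | 0.08 | 1.92 | 96% |

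**How full the row is early.** The chance that at least 9 of 10 children already have the term, 10·e⁹(1 − e) + e¹⁰, is 27% at e = 76%, 70% at e = 89% and 94% at e = 96%.

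If children with an early event are also more prone to a late one, the hidden share exceeds e. If they are less prone, it falls below e.

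**What still shows.** A term new to the child appears in its PT row. A later episode that is more severe or more related replaces the first in the maximum-severity or maximum-relationship table. An equally severe, equally related repeat changes nothing.

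**The case against.** The case against is substantial, and much of it limits the point.

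- **Phase is undefined.** The readable protocol text names no phases, and the flowchart is not available. The same paragraph speaks of continuous analysis from before gene therapy to study completion, and the SAP does split events at infusion. A reader might infer that the protocol requires cuts at week 6 and month 12. It does not; any cut-points are a proposal. What stands is that one cut at infusion leaves 36 months undivided.
- **Other outputs carry time.** Haematology and biochemistry, vital signs and physical examination are given by visit (SAP 8.4.4 to 8.4.6). Severe and opportunistic infections are counted as events, with separate rates for the first 12 months and for years 2 and 3 (SAP 8.3.2.3). Integration-site dominance is by visit (SAP 8.3.3.5). It would therefore be wrong to infer that conditioning toxicity cannot be separated from product toxicity at all; that holds only for the AE and SAE tables. The by-visit outputs carry no AE causality, and the first-year infection rate still pools the early weeks with later months.
- **Vector-specific harm is not masked at PT level.** Lympho- or myeloproliferation would normally be a new PT, and Protocol 8.8 and 11.4.3 deal with oncogenesis and proliferation separately.
- **Causality helps to some extent.** Relationship is graded against the product (Protocol 11.2), so an event blamed on busulfan can be graded unlikely and stay out of the treatment-related tables. Protocol 10.8 says "NIMP suspected Adverse Drug Reactions (ADR) or side effects will be reported through the yellow card system". A reader might infer that such events leave the dataset, but Protocol 11.2 sends all adverse events to the eCRF whatever their cause. What is missing is a positive attribution to busulfan.
- **The early rates are uncertain.** It is tempting to say that nine of ten children fill these rows within weeks. The 88% to 96% figures are adult label data, and the paediatric 89% is a composite rather than one PT. Abnormal test results need not be recorded as AEs. Protocol 9.1.3 reports no toxicity in two children at 5.1 mg/kg. The documents support a range, not that figure.
- **Event counts may be intended.** The mention of frequency in SAP 8.4.1.2 could mean this, but it conflicts with the once-only rule and needs settling.

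**Conclusion.** The mismatch is real and rests on no numerical assumption: the protocol promises safety by study phase, and the SAP's AE and SAE tables have no division after infusion. Combined with once-per-child counting, this hides later repeats of a term unless they are more severe or more related.

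The size depends on the early rate of each term. Under independence, 39% to 96% of late same-term cases would leave the incidence row unchanged across the Appendix 6 rates. The early rate in this non-myeloablative setting is unknown, and the late rate is not given. The other planned outputs cover part of the gap. This is a correction the SAP should make; it does not show that the safety evaluation as a whole fails.

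**What to change.** In SAP 8.4.1, define the study phases, with cut-points chosen by the sponsor. One workable set is conditioning to infusion, infusion to the 6-week visit, week 6 to month 12, and months 12 to 36.

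- Tabulate treatment-emergent AEs and SAEs by phase, counting each child once per SOC and PT within a phase. Use children still followed at the start of that phase as the denominator.
- Add the number of events beside the number of children, and reword the once-only rule so that it applies to the child count alone.
- State whether events between conditioning and infusion, which fall outside the treatment-emergent definition, get their own table or stay in the listing.
- Keep the pooled 0 to 36 month tables as a supplement.

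AE reporting is scheduled from the treatment column to month 36 (Protocol Appendix 5), so the cost is SAP wording and programming on dates already collected. The downside is more tables with small cells.

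A separate field for relationship to busulfan is optional and not part of this fix. SAP 7.1 describes the 10 on-study children as already recruited, so it would probably require retrospective, open-label re-grading.

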#### **Efficacy**

##### Primary Endpoints

Statistical methodologies for comparing gene therapy to historical controls at all stages will be descriptive in nature and will utilize the following approaches:

1. OS and EFS will be described using Kaplan-Meier curves for patients treated with investigational gene therapy product and HSCT, respectively, and statistically compared by the log-rank test and proportional hazards models (where applicable).
2. OS and EFS rates post treatment will be described by group and their differences between groups presented along with associated exact binomial confidence intervals.

### Main Secondary Endpoint

Percentage of subjects requiring immunoglobulin replacement therapy will be provided for each cohort (See Overview Section above) along with associated, two-sided, exact binomial, 95% confidence intervals.

The detailed statistical procedures will be provided in the statistical analysis plan (SAP).

## **9 Safety issues related to the gene therapy protocol**

### **9.1 Risks**

#### **9.1.1 Venepuncture**

Hazards associated with blood drawing are those associated with venepuncture and, those associated with the loss of red blood cells as a result of removal of blood from the procedures described in this protocol. Risks of venepuncture are pain, the potential for formation of a haematoma at the site of the needle stick and a small potential for infection at the site of needle stick. Occasionally, individuals having venepuncture may faint as a result of a vasovagal reaction to the procedure. These risks will be minimised by carefully preparing the site of needle puncture with alcohol swab, by using the smallest size needle required for the procedure, and by having the patient lie down or sit as appropriate for 5 or 10 minutes after venepuncture. The major risk of repeated blood drawing is anaemia from removal of red blood cells. To minimise this risk the amount of blood drawn for all purposes will be adjusted so as not to exceed the guidelines of 450 ml or 7.5 ml/kg (whichever is less) over any six-week period.

#### **9.1.2 Infection**

Withdrawal of PEG-ADA can have adverse effects on immunity, as well as on other organ systems. Once PEG-ADA is withdrawn, the numbers of circulating T, B, and NK lymphocytes will decline and may remain low for several months until the autologous transplant of gene-corrected CD34+ cells leads to immune reconstitution. It is possible that a severe infection may develop during this time and this could even be fatal if it does not respond to therapy. If immunity is severely decreased after discontinuation of enzyme replacement therapy and the subject experiences multiple or serious infections, then therapy may have to be resumed.

It is also possible that the cells for infusion could become infected with bacteria or fungus during the growth period in the laboratory. If there is any evidence of infection of the cells with unwanted agents and busulfan has already been administered, the cells will be returned to the subject with appropriate antibiotic cover. If the infection significantly affects viability (to a total cell dose of  $<0.5 \times 10^6/\text{kg}$ ) then transduced cells will not be returned and the back-up

bone marrow will be infused. However, there is a remote chance that subjects could acquire a bacterial or fungal infection from the re-infused cells (this also applies to the back-up cells, if administered).

### **9.1.3 Busulfan toxicity**

Busulfan has been widely used for myeloablation in bone marrow transplantation and has a well-described toxicity profile. When busulfan is used at high doses (16 mg/kg, which translates to approximately  $40 \text{ mg/m}^2 \times 16 \text{ doses}$ ) along with cyclophosphamide, as administered prior to allogeneic bone marrow transplantation, significant toxicity including thrombocytopenia and neutropenia have occurred, busulfan-related seizures and emesis may occur and are largely preventable with prophylactic medication. Rarely, veno-occlusive disease and pulmonary fibrosis (the latter two toxicities seen with busulfan/cyclophosphamide combinations) have been described. However, the nature and extent of toxicity resulting from low-dose busulfan (4mg/kg iv. total dose) in a paediatric population are not known. A recent report in ten ADA-SCID children demonstrated evidence of neutropenia but suggested no limiting toxicity with 4 mg/kg (Aiuti, A et al., 2002, 2009). Our own experience (of 3 patients) has shown no significant toxicity. The complications of high dose busulfan in combination with other chemotherapy drugs have not been seen in any of the more than 25 ADA-deficient patients treated using low dose busulfan. Busulfan is mutagenic (a clastogen, inducing DNA damage) and another potential cause for cancer in this study group. Although busulfan is frequently used in combination with cyclophosphamide in the clinical setting, there is the risk that it independently can cause cancer, even with the low dose proposed in this study.

The dosage schedule in this study is based on the differential clearance of busulfan in children of different weights. There is no evidence for any greater toxicity as a result of this weight adjusted dosing schedule. In two patients treated off trial on a compassionate basis and who received 5.1mg/kg of iv busulfan, no toxicity was seen.

